Appendix 2 – Quality of Life assessment / Anti-Clot Treatment Scale (ACTS)

During the past 4 weeks	i
-------------------------	---

- 1. How much does the possibility of bleeding as a result of anti-clot treatment limit you from taking part in vigorous physical activities? (e.g. exercise, sports, dancing, etc.).
- 2. How much does the possibility of bleeding as a result of anti-clot treatment limit you from taking part in your usual activities? (e.g. work, shopping, housework, etc.).
- 3. How bothered are you by the possibility of bruising as a result of anti-clot treatment?
- 4. How bothered are you by having to avoid other medicines (e.g. aspirin) as a result of anti-clot treatment?
- 5. How much does anti-clot treatment limit your diet? (e.g. food or drink, including alcohol).
- 6. How much of a hassle (inconvenience) are the daily aspects of anti-clot treatment? (e.g. remembering to take your medicine at a certain time, taking the correct dose of your medicine, following a diet, limiting alcohol, etc.).ù
- 7. How much of a hassle (inconvenience) are the occasional aspects of anti-clot treatment? (e.g. the need for blood tests, going to or contacting the clinic/doctor, making arrangements for treatment while travelling, etc.).

Now I want to ask you about daily and occasional aspects of your anticoagulation therapy during the past 4 weeks

8. How difficult is it to follow your anti-clot treatment?				
9. How time-consuming is your anti-clot treatment?				
10. How much do you worry about your anti-clot treatment?				
11. How frustrating is your anti-clot treatment?				
12. How much of a burden is your anti-clot treatment?				
13. Overall, how much of a negative impact has your anti-clot treatment had on your life?				
14. How confident are you that your anti-clot treatment will protect your health? (e.g. prevent blood clots, stroke, heart attack, DVT, embolism)				
15. How reassured do you feel because of your anti-clot treatment?				
16. How satisfied are you with your anti-clot treatment?				
17. Overall, how much of a positive impact has your anti-clot treatment had on your life?				
Copyright ©				
Copyright of the ACTS instrument is held by Bayer AG, Germany (2006). All rights				

reserved. For information on or permission to use, please contact Mapi Research Trust; http://www.mapi-trust.org.

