## 9.7 Handling of data, dropouts and missing values

For the Burden score of ACTS scale, no imputation on missing data will be applied if  $\geq 7$  items are incomplete; otherwise, the Burden score is calculated as the mean of the complete items score x 12. For the Benefit score of ACTS scale, no imputation on missing data will be applied if  $\geq 2$  items are incomplete; otherwise, the Burden score is calculated as the mean of the complete items score x 3.

In the situation where the event date is partial or missing, the date will appear partial or missing in the listings, and any corresponding durations will be presented based on the imputations specified in Section 12 “Partial Date Conventions”.

Other missing data will not be replaced.

The number of patients with missing data will be presented under the “Unknown” category.

Missing values will be included in the denominator count when computing percentages.

When continuous data are being summarized, only the non-missing values will be evaluated for computing summary statistics.

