- Quality of life evaluation (ACTS Scale) (see Appendix 2 of the study protocol): The ACTS is a 17-item, patient-reported measure of satisfaction with anticoagulant treatment. It includes 13 items concerning the burdens of anticoagulant treatment (items 1–12 plus 1 global question about burdens) and 4 items concerning the benefits of anticoagulant treatment (items 14–16 plus 1 global question about benefits). Each of the items is scored on a 5-point Likert scale (1 = not at all; 2 = a little; 3 = moderately; 4 = quite a bit; 5 = extremely). The Burden score was calculated as the sum of questions 1 to 12 subtracted from 60, with a higher score suggesting greater satisfaction with treatment. The Benefit score was calculated as the sum of questions 14 to 16, again with a higher score suggesting greater satisfaction. The Burden subscale can take values of 12-60 and the Benefit subscale score ranges from 3 to 15. Questions 13 and 17 are excluded from the subscale calculations.

For the Burden score, no imputation on missing data will be applied if  $\geq 7$  items are incomplete; otherwise, the Burden score is calculated as the mean of the complete items score  $\times 12$ .

For the Benefit score, no imputation on missing data will be applied if  $\geq 2$  items are incomplete; otherwise, the Burden score is calculated as the mean of the complete items score  $\times 3$ .

Default summary statistics will be presented for each of the two subscales at Visit 5. For each of the subscales, a linear effects model will be estimated with treatment group, center, symptomatic vs unsuspected VTE and active cancer vs history of cancer as dummy fixed effects. The least square means for Apixaban and Dalteparin, with 95% CIs and p-value will be presented. The difference between the least squares means for Apixaban and Dalteparin will be calculated along the 95% CI and p-value.

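### The ACTS Burden score runs in opposite directions for complete and incomplete forms, and its formula cannot give the stated 12–60 range

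*SAP*

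**What the plan says.** SAP 10.8.2 scores every ACTS item on one five-point scale: "1 = not at all; 2 = a little; 3 = moderately; 4 = quite a bit; 5 = extremely". It describes no reverse-coding of items. Items 1 to 12, listed in Protocol Appendix 2, are all negatively worded; item 12, for example, asks "How much of a burden is your anti-clot treatment". A higher raw answer therefore means more burden.

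For a complete form, "The Burden score was calculated as the sum of questions 1 to 12 subtracted from 60". The SAP also fixes the direction: larger values are meant to indicate a more satisfied patient. The same paragraph gives the possible values: "The Burden subscale can take values of 12-60 and the Benefit subscale score ranges from 3 to 15".

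For an incomplete form, SAP 9.7 leaves the Burden score unimputed when seven or more items are blank; "otherwise, the Burden score is calculated as the mean of the complete items score x 12". The corresponding Benefit sentence covers a form with one of its three items blank, but it names the wrong subscale: "otherwise, the Burden score is calculated as the mean of the complete items score x 3". SAP 10.8.2 repeats both missing-item rules.

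Each subscale then enters a linear model that yields least-squares means by arm, their difference, a 95% confidence interval and a p-value.

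**The concern.** The formula, the range, the direction and the missing-item rule for the Burden score cannot all be true. The subtraction from 60 reverses the scale for complete forms, and the rule for incomplete forms contains no subtraction. A satisfied patient who skips one item would then be recorded as dissatisfied, and the reverse for a dissatisfied patient.

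ACTS is the only patient-reported outcome among the endpoints in Protocol 5.1 and SAP 9.12.2. It is also where the trial would show whether the oral route is more convenient for patients, and convenience is part of the argument for a relatively large margin in Protocol 10.3 and SAP 9.5. Pooling scores of opposite meaning can hide a real difference between arms, or produce one if blank items are more common in one arm. The trial is open-label (SAP 6.7), so a choice among incompatible scoring rules should not be left to the programming stage.

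**Working it through.** **Inputs.** Twelve items, each scored 1 to 5 (SAP 10.8.2). Complete-form rule: 60 − S, where S is the sum of items 1–12 (SAP 10.8.2). Rule for one to six blanks: 12 × m, where m is the mean of the answered items (SAP 9.7 and 10.8.2). Stated range 12–60, higher meaning more satisfied.

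**Step 1: try to reproduce the stated range.** S runs from 12 × 1 = 12 to 12 × 5 = 60.

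| Reading | Lowest | Highest | Range 12–60? | Higher = more satisfied? |
|---|---|---|---|---|
| 60 − S (as written) | 60 − 60 = 0 | 60 − 12 = 48 | no | yes |
| S, no subtraction | 12 | 60 | yes | no |
| 72 − S | 72 − 60 = 12 | 72 − 12 = 60 | yes | yes |

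The written formula does not reproduce 12–60: values 49–60 cannot occur, and values 0–11 lie below the stated minimum. The Benefit range does reproduce (3 × 1 = 3 to 3 × 5 = 15), so the range fault is specific to Burden.

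**Step 2: compare the two rules for the same answers.** A complete form with item mean m scores 60 − 12m; a form with a blank and the same mean scores 12m.

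| Item mean m | Complete: 60 − 12m | One blank: 12m | Shift |
|---|---|---|---|
| 1 | 48 | 12 | −36 |
| 2 | 36 | 24 | −12 |
| 2.5 | 30 | 30 | 0 |
| 3 | 24 | 36 | +12 |
| 4 | 12 | 48 | +36 |
| 5 | 0 | 60 | +60 |

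The rules agree only at m = 2.5. Changing 60 to 72 for complete forms alone would not cure this: at m = 1 the scores would be 60 and 12.

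**Step 3: effect on the comparison, equal incompleteness.** Suppose a share p of forms in each arm has one to six blanks, unrelated to the answers. An arm's expected score is (1 − p)(60 − S) + pS, so the between-arm difference is the complete-form difference times (1 − p) − p = 1 − 2p. Take assumed item means of 1.5 and 2.0 (S = 18 and 24, scores 42 and 36, true difference 6):

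| p | Arm means | Difference | Factor |
|---|---|---|---|
| 0% | 42.0, 36.0 | 6.0 | 1.00 |
| 5% | 40.8, 35.4 | 5.4 | 0.90 |
| 10% | 39.6, 34.8 | 4.8 | 0.80 |
| 20% | 37.2, 33.6 | 3.6 | 0.60 |
| 50% | 30.0, 30.0 | 0.0 | 0.00 |

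**Step 4: unequal incompleteness with no true difference.** The gap between the two rules is (60 − S) − S = 60 − 2S. If the incomplete share differs by 5 percentage points, the false difference is 0.05 × (60 − 2S):

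| S (same in both arms) | Gap 60 − 2S | False difference |
|---|---|---|
| 12 | 36 | 1.8 |
| 20 | 20 | 1.0 |
| 24 | 12 | 0.6 |
| 30 | 0 | 0.0 |
| 36 | −12 | −0.6 |

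A positive value means that the arm with more blanks looks worse. With S = 18 and incomplete shares of 5% and 15%, the arm means are 40.8 and 38.4, a false difference of 2.4 points.

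**The case against.** The best defence is that 12 times the mean is the usual prorated item sum, and that SAP 9.7 offers it as an imputation. If it is then subtracted from 60, complete and incomplete forms run the same way. But both sections call the prorated value the Burden score itself, and under this reading the range is still 0–48. A second defence is that items are reverse-coded before scoring. Then 12 times the mean fits both the range and the direction, but 60 minus the sum runs backwards and still gives 0–48; neither document mentions such coding. No single reading satisfies all four statements.

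Several limits on the consequences do stand:

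- The range error alone shifts every complete form by a constant 12 points. It misplaces the reported means on the stated scale but does not change the between-arm difference, its interval or its p-value. Only the reversal can bias the comparison.
- The 1 − 2p factor needs equal incompleteness in both arms, unrelated to the answers. Otherwise the difference can grow: with S = 18 and 24 and incomplete shares of 0% and 10%, the means are 42.0 and 34.8, a difference of 7.2 against a true 6.
- The false difference depends on the item sum as well as on p, and the documents give neither.
- The margin sections do not cite ACTS, so the justification of 2.00 does not depend on its result.
- The Benefit sentence opens by naming Benefit and multiplies by 3, so the word Burden there is a clerical slip.

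**Conclusion.** The point holds: the scoring rule is wrong as written. The range contradiction and the reversal follow from the SAP's own text and need no assumption beyond taking the sentences literally. The same answers can move by as much as 36 points at the satisfied end (48 to 12) and 60 points at the dissatisfied end (0 to 60) because one item is blank.

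The effect on the treatment comparison depends on the share of forms with one to six blanks. For assumed equal shares of 5% to 20%, unrelated to the answers, the difference shrinks by 10% to 40%. For an assumed 5-point imbalance and an item sum of 20, a false difference of 1 point appears; over item sums of 12 to 36 it runs from 1.8 to −0.6. The damage is confined to one secondary endpoint. This should be corrected, but it does not threaten the primary result.

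**What to change.** In SAP 9.7 and 10.8.2:

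- Complete form: Burden = 72 − sum of items 1–12, range 12–60, higher meaning more satisfied.
- One to six blanks: Burden = 72 − 12 × mean of the answered items among 1–12.
- One blank among items 14–16: Benefit (not Burden) = 3 × mean of the answered items.

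Answering 1 throughout then gives 60 and answering 5 throughout gives 12, with or without a blank.

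If 60 minus the sum is kept, state the range as 0–48 and use 60 − 12 × mean for incomplete forms. The first option preserves the stated range and direction. Either should be checked against the instrument's own scoring instructions, available through the rights holder named in Protocol Appendix 2.

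The cost is about five short sentences across the two sections (the formula or the range once, the two missing-item rules twice each) and a line of code. No new data are needed.

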## 10.9 Safety analyses

The analysis of safety will be based on the Safety Population, comparing patients in the two randomized arms: apixaban vs. dalteparin. Analysis of safety will include all events recorded during the treatment period and up to 30 days after the last study dose intake,

To assess the bleeding risk associated with the use of either apixaban or dalteparin, we will include all bleeding events that occur during the on treatment period, which is the classical period for the evaluation of safety. On-treatment bleeding has been defined as occurring during treatment with the assigned study drug or up to 72 hours after the last dose intake.

Concerning bleeding, secondary analyses will be performed:

- 1) To determine how apixaban compares to dalteparin therapy based on a reduction in major bleeding events over 6 months of therapy;
- 2) To determine how apixaban compares to dalteparin therapy in the combined endpoint of adjudicated major/CRNM bleeding over 24 weeks of therapy;
- 3) To determine how apixaban compares to dalteparin therapy based on a reduction in GI bleeding events over 6 months of therapy.

The number and the percentage of patients with bleeding events as well as the number of events will be presented in summary statistical tables.

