### **9.2 General methodology**

All data summaries and listings will be performed using the SAS System version 9.4 under Windows 10 PRO operating system. The statistical analysis will be performed by SPARC Consulting, Milan, Italy on behalf of Exom Group, Milan, Italy.

Continuous-scaled variables will be summarized with means, medians, standard deviations, quartiles, and minimum and maximum values. Categorical variables will be summarized using patient counts and percentages.

Two-sided 95% confidence intervals for proportions and means will also be produced, where clinically appropriate.

The statistical testing will be conducted at the  $\alpha$  level of 0.05 (two-sided) unless differently specified (primary end-point analysis). Confidence intervals will be calculated at the confidence level of 95%.

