**9.12.3 Primary safety endpoint**

The primary safety endpoint is the proportion of subjects with major bleeding, defined (as per ISTH guidelines), as acute clinically overt bleeding associated with one or more of the following:

- a decrease in hemoglobin of 2 g/dL or more;
- a transfusion of 2 or more units of packed red blood cells;
- bleeding that occurs in at least one of the following critical sites [intracranial, intra-spinal, intraocular (within the corpus of the eye; thus, a conjunctival bleed is not an intraocular bleed), pericardial, intra-articular, intramuscular with compartment syndrome, or retroperitoneal];
- bleeding that is fatal (defined as a bleeding event that the independent Clinical Event Adjudication Committee determined was the primary cause of death or contributed directly to death);
- bleeding that necessitates surgical intervention.

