## **10 Statistical Analysis**

### **10.1 Disposition of patients**

Tables and data listings will be presented for ENR population.

The number of subjects enrolled into the study, and the number of subjects enrolled but not randomized together with the reasons for not being randomized will be summarized.

An individual data listing of the patients who did not satisfy the eligibility criteria will be presented (screening log).

The frequency of patients enrolled in each site will be tabulated by randomized treatment group and for all randomized patients combined.

A summary of analysis populations and an individual data listing of the reasons for patients' exclusion from each population will be presented.

The summaries of disposition described below will also be presented by randomization stratification factor - index event.

The number of treated patients, the number of patients who completed 6 months of study treatment, and the number of subjects discontinuing study therapy together with the reasons for discontinuation will be summarized by treatment group.

The reasons for discontinuation will be taken from the End-of-Treatment Status page of the CRF.

Discontinuations from study drug due to AEs will further be summarized by the AE type: ipsilateral proximal DVT lower limbs, contralateral proximal DVT lower limbs, DVT upper limbs, PE, bleeding, acute myocardial infarction (MI), ischemic stroke, other venous thromboembolic events, other arterial thromboembolic events, and other adverse events.

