#### 10.8.2 Analysis of secondary endpoints

For the secondary efficacy endpoints, analyses will be performed using the mITT analysis set.

- The individual components of the primary efficacy outcome (Proximal DVT of the lower limbs (symptomatic or unsuspected), DVT of the upper limb (symptomatic), and PE (symptomatic or unsuspected)): The same competing risk model defined in paragraph 10.8.1 for the analysis of primary efficacy variable will be employed for the analysis of the time (in days) from randomization to the first recurrent event among those included in the primary efficacy outcome recurrent (see Paragraph 9.12.1). The apixaban-to-comparator Hazard Ratio adjusted for the competing risk of death unrelated to VTE will be computed with associated two-sided 95% confidence interval. If neither the event of interest nor a competing event occurred within the 6-month follow-up, the patient will be censored at 6-month follow-up.
- Symptomatic recurrence of VTE: The same competing risk model defined in paragraph 10.8.1 for the analysis of primary efficacy variable will be employed for the analysis of the time (in days) from randomization to the first symptomatic recurrent thromboembolic event. The apixaban-to-comparator Hazard Ratio adjusted for the competing risk of death unrelated to VTE will be computed with associated two-sided 95% confidence interval. If neither the event of interest nor a competing event occurred within the 6-month follow-up, the patient will be censored at 6-month follow-up.
- Composite of primary efficacy outcome plus major bleeding: The competing risk model defined in paragraph 10.8.1 for the analysis of primary efficacy variable will be employed for the analysis of the time (in days) from randomization to the composite of primary efficacy outcome (see Paragraph 9.12.1) plus major bleeding. The apixaban-to-comparator Hazard Ratio adjusted for the competing risk of death unrelated to VTE or major bleeding will be computed with associated two-sided 95% confidence interval. If neither the event of interest nor a competing event occurred within the 6-month follow-up, the patient will be

censored at 6-month follow-up.

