- Death due to any cause (OS): Overall Survival is defined as the time (in days) from randomization to the date of death for any cause. OS will be estimated according to Kaplan-Meier calculating median, first and third quartiles with the respective 95% confidence intervals. Kaplan-Meier plots with a 95% CI will be prepared. OS in the two treatment groups will be also compared by means of a Cox's proportional hazard model with treatment group, center, symptomatic vs unsuspected VTE and active cancer vs history of cancer as dummy covariates. The apixaban-to-comparator Hazard Ratio will be computed with associated two-sided 95% confidence interval. Subjects still surviving at the end of the study will be censored at the date of the last contact.
- Composite of primary efficacy outcome plus major bleeding plus death due to any cause: Event-free-survival is defined as the time (in days) from randomization to the date of event (composite of primary efficacy outcome plus major bleeding plus death due to any cause). Event free survival will be estimated according to Kaplan-Meier calculating median, first and third quartiles with the respective 95% confidence intervals. Kaplan-Meier plots with a 95% CI will be prepared. Event-free-survival in the two treatment groups will be compared by means of a Cox's proportional hazard model with treatment group, center, symptomatic vs unsuspected VTE and active cancer vs history of cancer as dummy covariates. The apixaban-to-comparator Hazard Ratio will be computed with associated two-sided 95% confidence interval. Subjects with no events at the end of the study will be censored at the date of the last contact.
- Composite of primary efficacy outcome plus death due to any cause: Event-free-survival is defined as the time (in days) from randomization to the date of event (composite of primary efficacy outcome plus death due to any cause). Event free survival will be estimated according to Kaplan-Meier and the event free survival in the two treatment groups will be compared by means of a Cox's proportional hazard model with treatment group, center, symptomatic vs unsuspected VTE and active cancer vs history of cancer as dummy covariates. The apixaban-to-comparator Hazard Ratio will be computed with associated two-sided 95% confidence interval. Subjects with no events at the end of the study will be censored at the date of the last contact.

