- Any fatal or not fatal cardiovascular event: The competing risk model defined in paragraph 10.8.1 for the analysis of primary efficacy variable will be employed for the analysis of the time (in days) from randomization to the occurrence of any fatal or not fatal cardiovascular event. The apixaban-to-comparator Hazard Ratio adjusted for the competing risk of death unrelated to cardiovascular event will be computed with associated two-sided 95% confidence interval. Number and percentage of events of interest, competing events and censored patients will be presented as summary of failure outcome. Degrees of freedom (DF), Wald Chi-square and the associated p-value derived from the PHREG model will be also presented. Subjects with no events at the end of the study will be censored at the date of the last contact.
- All venous thromboembolic events (including splanchnic vein thrombosis and cerebral vein thrombosis): The same competing risk model defined in paragraph 10.8.1 for the analysis of primary efficacy variable will be employed for the analysis of the time (in days) from

randomization to thromboembolic events at sites other than DVT and PE. The apixaban-to-comparator Hazard Ratio adjusted for the competing risk of death unrelated to venous thromboembolic events will be computed with associated two-sided 95% confidence interval. Number and percentage of events of interest, competing events and censored patients will be presented as summary of failure outcome. Degrees of freedom (DF), Wald Chi-square and the associated p-value derived from the PHREG model will be also presented. Subjects with no events at the end of the study will be censored at the date of the last contact.

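### Major bleeding, the primary safety outcome, is specified only as a crude on-treatment proportion; no between-arm effect measure that accounts for time on drug is named

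*SAP*

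**What the plan says.** SAP 9.12.3: "The primary safety endpoint is the proportion of subjects with major bleeding". SAP 5.2 and 10.9 count bleeding on treatment, up to 72 hours after the last dose, and 10.9 uses the safety set.

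SAP 10.9 then lists comparative aims for bleeding. One is to compare the arms "based on a reduction in major bleeding events over 6 months of therapy". The output named is: "The number and the percentage of patients with bleeding events as well as the number of events will be presented in summary statistical tables". Protocol 10.7 adds no effect measure for bleeding.

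SAP 9.2 sets a default two-sided 0.05 level and says: "Two-sided 95% confidence intervals for proportions and means will also be produced, where clinically appropriate".

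SAP 10.8.2 is more specific for other outcomes:
- for recurrent VTE plus major bleeding: "Hazard Ratio adjusted for the competing risk of death unrelated to VTE or major bleeding will be computed", with a 95% confidence interval;
- for the outcome "Composite of primary efficacy outcome plus major bleeding plus death due to any cause": a Cox hazard ratio with a 95% confidence interval;
- for cardiovascular events: "Hazard Ratio adjusted for the competing risk of death unrelated to cardiovascular event will be computed", again with a 95% confidence interval.

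On persistence, SAP 10.1 says that "the number of subjects discontinuing study therapy together with the reasons for discontinuation will be summarized by treatment group", and SAP 10.7 summarizes treatment duration by arm.

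**The concern.** The SAP states a comparison of bleeding between arms but not how it will be made. Nothing says whether the comparison is a risk ratio, a risk difference, a rate ratio or a hazard ratio. Nor is there a censoring rule or a way of handling death for major bleeding alone. In an open-label trial, a measure left open can be chosen after the data have been seen.

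The one measure that is specified, the proportion, depends on exposure. A patient who stops drug at month 2 contributes about two months in which a bleed can be counted; a patient who completes contributes six. If more patients stay on one drug than on the other, the arm with longer exposure shows more bleeds even when the bleeding hazards are identical.

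The comparison is of an oral drug with a daily injection, and SAP 9.5 defends a wide efficacy margin partly by pointing to potential gains in safety and compliance. Readers will therefore set the bleeding result beside the efficacy result. A difference in persistence would be visible in the tables of disposition and duration, but nothing in the bleeding comparison would account for it.

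**Working it through.** **The plan's own figure.** Protocol 10.1 and SAP 9.3 allow for 40% drop-out, uniform over follow-up, with a mean of 3 months. Lost patient-time is 0.40 × 3/6 = 20%, and 934/(1 − 0.20) = 1167.5, i.e. 1168. Both figures reproduce. The plan gives no power or precision figure for major bleeding.

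**Inputs for the illustration.**
- From the documents: 40% drop-out, uniform; 72-hour window (3 days); 6 months taken as 180 days.
- Assumed: the 40% describes stopping of study drug; six-month major bleeding risk p = 4% under full treatment (6% as a check); equal bleeding hazards in both arms; the splits of stopping between arms.

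**Constant hazard.** With L = −ln(1 − p)/180 and d the fraction who stop early:

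crude risk = (1 − d)(1 − e^(−180L)) + d × mean over u uniform on 0–180 of [1 − e^(−L·min(u+3, 180))]

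At p = 4% the first bracket is 4.00% and the mean over early stoppers is 2.08%.

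| Stopping, arm A vs arm B | Risk A | Risk B | Crude ratio |
|---|---|---|---|
| 40% vs 40% | 3.232% | 0.6×4.00 + 0.4×2.08 = 3.232% | 1.00 |
| 35% vs 40% | 0.65×4.00 + 0.35×2.08 = 3.328% | 3.232% | 1.03 |
| 30% vs 40% | 0.7×4.00 + 0.3×2.08 = 3.424% | 3.232% | 1.06 |
| 20% vs 40% | 0.8×4.00 + 0.2×2.08 = 3.616% | 3.232% | 1.12 |
| 30% vs 50% | 3.424% | 0.5×4.00 + 0.5×2.08 = 3.040% | 1.13 |

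At p = 6% the ratios agree to two decimals. Events per day at risk give 1.00 in every row. The formula stops counting at Day 180 for simplicity. Without that cap, mean counted time is (1 − d)×183 + d×93 days: 147 at 40% and 156 at 30%, a ratio of 156/147 = 1.06, so the cap does not drive the result.

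**Early peak.** Both regimens start at a higher dose (Protocol 6.2), so bleeding may be concentrated early. Assume a month-1 hazard three times the later one, with p still 4%. The mean over early stoppers becomes 2.50%.
- 30% vs 40%: (0.7×4.00 + 0.3×2.50)/(0.6×4.00 + 0.4×2.50) = 3.55/3.40 = 1.04.
- 20% vs 40%: (0.8×4.00 + 0.2×2.50)/3.40 = 3.70/3.40 = 1.09.
- Events per day now drift too, to 0.99 and 0.97, because the arm that stops earlier contributes relatively more high-risk early days.

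A Cox hazard ratio compares patients at the same time since start, so it remains 1.00 under either hazard shape if stopping is uninformative. This is the reason to prefer it to a simple rate.

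**Precision.** For p of 3% to 6% (assumed) and 40% stopping in both arms, on-treatment risks are about 2.40% and 4.81%. That gives 1168 × 0.0240 = 28 to 1168 × 0.0481 = 56 major bleeds. The 95% interval is then the hazard ratio times or divided by exp(1.96 × 2/√28) = 2.10 to exp(1.96 × 2/√56) = 1.69.

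**48 against 72 hours.** The protocol synopsis bases safety summaries on last dose plus 48 hours; the SAP uses 72 hours for bleeding. Uncapped mean counted time is 0.6×180 + 0.4×90 = 144 days, plus 2 = 146 or plus 3 = 147: 0.7%. Capped at Day 180 it is 144.8 against 145.2 days: 0.3%.

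**The case against.** An on-treatment proportion is a legitimate safety summary. Exposure and discontinuation are tabulated by arm, SAP 9.2 supplies a default test level and intervals for proportions, and the table shells, a separate document not available here, may show more. The numerical shift rests on stacked assumptions. The documents predict no arm difference in stopping. Much of the 40% could be death, since Protocol 6.5.1 lists death as a permanent discontinuation and the two cited LMWH trials had six-month mortality of 32% and 40%. A shift of 3% to 6% is small beside a confidence interval that spans a factor of 1.7 to 2.1 on either side.

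All of that stands, and it limits the size of the point. It does not fill the gap: a default alpha and an interval for a single proportion are not a between-arm measure, and the choice of measure belongs in the SAP text.

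A reader might infer three stronger things that the documents do not support.
- That the bleeding comparison will be biased against one drug. This needs unequal persistence, which is only assumed here.
- That the 48-hour and 72-hour windows produce materially different results. They differ by 0.3% to 0.7% in counted time. The 48 hours appear only in the synopsis, Protocol 10.4 and 10.7 set no hour limit, and the SAP is consistent at 72.
- That the 30-day tabulation of bleeding among adverse events is a rival, unlabelled primary count. SAP 10.9.1 already says that those summaries are descriptive.

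**Conclusion.** The point holds as a cheap improvement. For major bleeding alone the SAP specifies a crude on-treatment proportion and event counts, states an aim to compare the arms, and names no effect measure, while it specifies hazard ratios for composites that contain major bleeding and for less prominent outcomes. That gap is textual and does not depend on any calculation.

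The possible distortion is modest. With equal, constant hazards and uniform stopping, the crude ratio is 1.00 if stopping is equal, 1.03 to 1.06 for a gap of 5 to 10 points, and 1.12 to 1.13 for a gap of 20 points. With an early bleeding peak, a 10-point gap (30% vs 40%) gives 1.04 and a 20-point gap (20% vs 40%) gives 1.09. The arm splits, bleeding risks and hazard shapes are assumptions, and the shift may be nil. No bleeding criterion enters the non-inferiority decision, so the primary conclusion of the trial is not at risk. The difference in windows is a matter of wording.

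**What to change.** In SAP 10.9, beside the number and percentage, prespecify on the safety set:

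1. Time to first adjudicated major bleed, and time to first event of the composite of major and clinically relevant non-major bleeding. Follow-up ends at last dose plus the on-treatment window. Do not cap it at Day 180: the end-of-treatment visit is at 6 months ± 7 days, so a cap would discard bleeds in patients still on drug.
2. A hazard ratio with 95% confidence interval from a cause-specific Cox model, and cumulative incidence curves with death as a competing event. Say why this differs from the Fine & Gray model used in 10.8: the question here is the bleeding rate while on drug.
3. The covariates. SAP 9.6 requires center, both stratification factors and their interaction in every Cox model. Either keep them, or state in 9.6 that center and the interaction are omitted for this model because events are few. With pooled sites of at least 12 patients there could be up to 97 groups (1168/12 = 97.3), against perhaps 28 to 56 bleeds.
4. A sensitivity analysis of all major bleeds to 6 months, whether or not the patient is still on drug.

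Wording: reconcile 48 hours in the protocol synopsis with 72 hours in SAP 5.2 and 10.9 so that both documents name one window. Reconcile 24 weeks (168 days) with 6 months in the list of bleeding aims in SAP 10.9; the text does not show which was meant.

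Cost: a few model runs and some text. No new data are needed, because patients who stop drug are followed to 7 months (Protocol 6.6) and major bleeds to 6 months are already required for a composite in SAP 10.8.2. The drawback is that censoring at drug stop may be informative; the sensitivity analysis in item 4 is there to show whether that matters.
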